8.4 Formulation of Test and Control Products

8.4.1 Formulation of Test Product

AK001 is a humanized IgG4 MAb directed against Siglec-8. AK001 Drug Product is supplied as a sterile liquid in a single-use 10R glass vial with a fill volume of not less than 10 mL. The product is stored at 2 to 8°C. The AK001 formulation is 15 ±1.5 mg/mL AK001 in 125 mM arginine, 80 mM sodium chloride, 20 mM succinate and 0.025% polysorbate 80 (w/v), pH 6.0, in sterile water for injection.

AK001 is administered by IV infusion. Dose preparation and administration details are provided in the study pharmacy manual.

8.4.2 Formulation of Control Product

The placebo is supplied as a sterile liquid in a single-use 10R glass vial with a fill volume of not less than 10 mL. The placebo contains 125 mM arginine, 80 mM sodium chloride, 20 mM succinate and 0.025% polysorbate 80 (w/v), pH 6.0, in sterile water for injection. The vial is indistinguishable from the AK001 active product. The placebo is stored at 2 to 8°C.

8.4.3 Packaging and Labeling

AK001 Drug Product and placebo are supplied as a sterile liquid in a single-use 10R glass vials with a fill volume of at least 10 mL. Each vial will be labeled with information required by the Food and Drug Administration (FDA) and according to pertinent European Union (EU) and national regulations, as appropriate for the country in which the study drug is being used.

Each carton (kit) of study drug will be labeled with the required FDA investigational use statement, a lot number, name of the Sponsor, and directions for storage.

8.5 Supply of Study Drug at the Site

The Sponsor (or designee) will ship study drug to the investigational sites. The initial shipment will occur after site activation (i.e., all required regulatory documentation has been received by the Sponsor and a contract has been executed).

8.5.1 Dosage/Dosage Regimen

AK001 25 mg and 250 mg and placebo will each be administered as a single IV infusion of over approximately 1 hour through a peripheral vein.

8.5.2 Preparation

Using the IXRS, the unblinded study pharmacist will prepare the AK001 or placebo for IV administration to each patient on Days 0, 21, and 49. Preparation of individual solutions for IV administration will be performed at the investigational site by the designated unblinded study pharmacist using the randomization code provided. Each vial is assigned a kit

number that can be associated with a treatment assignment in the system by a list accessible to an unblinded monitor, independent of the study. The diluted IV solution container will be identified with the patient identifier, but will not indicate the treatment assignment. Appropriate aseptic technique will be used, and the drug will be prepared according to the pharmacy manual for AK001.

8.5.3 Administration Instructions

Specific instructions for study drug administration are detailed in the pharmacy manual. In general, AK001 and placebo will be infused over approximately 1 hour through a peripheral vein. The IV will be kept open before and after the infusion with sufficient quantities of 0.9% saline to assure it remains patent.

Each patient will remain at the Investigator site for a safety observation period of at least 8 hours following the end of each infusion. At the discretion of the Investigator, a longer monitoring period, if needed, before the patient is discharged, may be implemented. Follow-up telephone calls will be made to the patient at 12 and 24 hours following the end of each infusion. Patients will be informed that, from discharge to the 24-hour telephone contact, they must be accompanied by another adult at all times, not travel alone or travel during bad weather, remain close to the location of the site, and have access to a telephone and transportation. If there are any safety concerns, enrollment will be put on hold, and a safety review meeting will occur.

The IV infusion may be interrupted for 5 to 30 minutes and the rate may be reduced and gradually increased in 15-minute intervals if a patient experiences infusion-related reactions. Acetaminophen and, if needed, a glucocorticoid (e.g., 125 mg methylprednisolone IV) may be administered to the patient if the patient experiences reactions that is considered mild to moderate (e.g., itching or a localized rash). If a patient experiences signs or symptoms of anaphylaxis, the patient will be treated with standard-of-care medications, such as diphenhydramine, acetaminophen, methylprednisolone, epinephrine, and other supportive measures along with cessation of the infusion. Administration will be discontinued if, in the opinion of the Investigator, the infusion cannot be restarted after 30 minutes for safety reasons.

8.6 Supply of Study Drug at the Site

AK001 (15 mg/mL) and placebo will be provided by the Sponsor in 10R single-use vials. Study drug may be prepared on the morning of Day 0. Any patient who is randomized but not treated will be replaced by another patient and new study drug will be prepared for the alternate patient.

8.6.1 Storage

AK001 and placebo will be stored by the investigational site at 2°C to 8°C under lock at each site's pharmacy room, pending drug preparation. Access will be restricted to designated study pharmacy staff. All clinical supplies will be temperature controlled and monitored. If the temperature of study drug storage in the clinic/pharmacy exceeds or falls

below this range, this will be reported to the Sponsor or designee and considered a deviation, and study drug should be quarantined until further notice from Sponsor.

8.7 Study Drug Accountability

The unblinded study pharmacist will keep accurate and current accounting of the preparation and dose of study drug for each patient, with sources and quantities of study drug received, quantities of study drug dispensed for and used by each individual patient specified, and quantities of study drug returned, if applicable. A drug dispensing and accountability log will be maintained by the unblinded study pharmacist.

8.8 Measures of Treatment Compliance

The study drug will be administered under supervision of the Investigator or designee. The calendar date and 24-hour clock times each infusion is initiated and concluded and, as necessary, interrupted and resumed will be documented in the eCRF.

9 STUDY PROCEDURES AND GUIDELINES

A Schedule of Events depicting the required procedures to be performed for the duration of the study is provided in [Table 1](#).

Prior to conducting any study-related activities, the ICF and any other required country-specific documents must be signed and dated by the patient.

9.1 Dietary and Lifestyle Restrictions

Patients will refrain from alcohol and strenuous exercise (e.g., heavy lifting, weight training, aerobics) for at least 48 hours prior to each blood collection for clinical safety laboratory tests.

Patients will be required to fast overnight (8 hours) from food and beverages other than water before blood is drawn for clinical safety laboratory tests. The duration of the fast should be no longer than the typical overnight sleeping period for the patient.

9.2 Clinical Assessments

9.2.1 Prior and Concomitant Medications

All prior medication and therapies received between 30 days before Screening and start of study drug will be documented at Screening and at Days -3, and pre-dose on Day 0.

All concomitant medication and concurrent therapies will be documented post-dose on Day 0 and on Days 14, 21, 49, 84, 112, and 168 or at Early Termination (ET). Dose, route, unit, frequency of administration, indication for administration, and dates of each medication will be recorded.

9.2.2 Demographics

Demographic information (date of birth, gender, and race) will be recorded at Screening.

9.2.3 Medical History

A medical history will be obtained at Screening and include all relevant medical history information (e.g., history of current disease, other pertinent respiratory system history, information regarding aspirin sensitivity [obtained in response to specific question(s) about aspirin sensitivity], and underlying diseases) for the 5 years before Screening.

9.2.4 Physical Examination

A complete PE will be performed by either the Principal Investigator or a qualified Sub-investigator at Screening. A complete PE will include the following body system or organ assessments: skin; head, eyes, ears, nose, and throat (HEENT); thyroid; lungs; cardiovascular system; abdomen; extremities; lymph nodes; and a brief neurological examination. Height (in cm) and weight (in kg) will be measured at Screening, and BMI will be calculated. Weight only will be measured on Day 0, Day 112, and Day 168 or ET. A symptom-directed PE, including assessments of possible infusion site reactions, will be performed by either the Investigator or a qualified Sub-investigator pre-dose (and post-dose as indicated) on Days 0, 21, and 49 and on Days 14, 84, 112, and 168 or ET. New abnormal PE findings must be documented and will be followed by the Investigator or qualified Sub-investigator at the next scheduled visit.

9.2.5 Vital Signs

Body temperature, supine systolic and diastolic blood pressure, pulse, and respiratory rate will be measured at Screening and on Days -3, 0, 14, 21, 49, 84, 112, and 168 or ET. On Days 0, 21, and 49, vital signs will be measured pre-dose, every 15 minutes after the start of infusion, and immediately following the end of infusion. All vital signs will be measured after the patient has been in the supine position for ≥ 5 minutes.

9.2.6 Electrocardiogram

A 12-lead ECG will be performed at Screening.

9.2.7 Fecal Collection

Fecal samples will be collected at Screening for ova and parasite tests.

9.2.8 Adverse Events

Information regarding AEs will be obtained from the time of the first study drug administration until completion of the last study-related procedure (Day 168 or ET). Information regarding serious adverse events (SAEs) will be obtained from the time the patient signs an ICF until completion of the last study-related procedure (Day 168 or ET).

Duration (start and stop dates and times), severity, outcome, treatment, and relation to study drug will be recorded on the eCRF.

9.3 Clinical Safety Laboratory Measurements

Blood and urine samples will be obtained for clinical safety laboratory tests (hematology, chemistries, and urinalyses) and for ADA as specified in [Table 1](#) and [Sections 9.3.2, 9.3.3, and 9.3.5](#). Blood for clinical safety laboratory tests will be collected following an overnight fast (8 hours) from food and beverages other than water. The duration of the fast should be no longer than the typical overnight sleeping period for the patient.

Certified laboratories will be used to process and provide results for the clinical safety laboratory tests. The Baseline laboratory test result will be defined as the last measurement prior to the first infusion of study drug.

For any laboratory test value outside the reference range that the Investigator considers clinically significant, the Investigator will:

- Repeat the test to verify the out-of-range value
- Follow the out-of-range value to a satisfactory clinical resolution

The Investigator will record as an AE any laboratory test value that (1) is confirmed and the Investigator considers clinically significant, (2) that requires a patient to be discontinued from the study, or (3) that requires a patient to receive treatment.

9.3.1 Serology

Blood will be obtained at Screening for HIV, HBV surface antigen, and HCV antibody testing.

9.3.2 Hematology

Blood will be obtained at Screening; on Day -3; pre-dose on Days 21 and 49, and on Days 14, 84, 112, and 168 or ET for a complete blood count (CBC) with differential: hemoglobin, hematocrit, red blood cell count, white blood cell (WBC) count, WBC differential, and platelet count.

9.3.3 Blood Chemistry Profile

Blood will be obtained at Screening; on Day -3; pre-dose on Days 21 and 49; and on Days 14, 84, 112, and 168 or ET for determination of serum sodium, potassium, chloride, bicarbonate, glucose, blood urea nitrogen, creatinine, creatinine kinase, aspartate aminotransferase (AST), alanine aminotransferase (ALT), alkaline phosphatase, total bilirubin, direct bilirubin, gamma-glutamyl transferase, albumin, and lactate dehydrogenase.

9.3.4 Pregnancy and Follicle-Stimulating Hormone Tests

For all female patients, blood will be obtained for a serum pregnancy test at Screening, and blood or urine is to be obtained for pregnancy tests on Day -3, pre-dose on Days 21 and 49, and on Day 168 or ET. Blood for FSH is to be obtained only at Screening to confirm postmenopausal status (FSH level >30 IU/L).

9.3.5 Urinalysis

Urine will be obtained at Screening; pre-dose on Days -3 and 49; and on Days 14, 84, 112, and 168 or ET for determination of color, specific gravity, pH, protein, glucose, ketones, and blood.

9.4 Anti-drug Antibodies

Blood will be collected for determination of ADA pre-dose on Day 0 and, should a related AE suspected of being associated with immunogenicity occur, post-dose, and on Days 112 and 168 or ET.

9.5 Pharmacokinetic Measurements

Blood samples for serum concentrations of AK001 will be obtained pre-dose on Days 0, 21, and 49 and on Days 14, 84, 112, and 168 or ET for PK analyses. AK001 concentrations will be determined by a central laboratory using an ELISA method. Specific information on PK collection, processing, storage, and shipment will be provided in a separate manual.

9.6 Efficacy Measurements

Specific information on the collection, processing storage, and shipment of samples will be provided in a separate manual.

9.6.1 Serum Samples for Total Immunoglobulin E

Blood will be collected for the testing of total IgE on Day -3.

9.6.2 Serum Samples for ImmunoCAP

Blood will be collected for the determination of allergen specific IgE on Day -3. Allergens to be used in testing are house dust mites (*Dermatophagoides farina* and *Dermatophagoides pteronyssinus*), birch, timothy grass (*Phleum pretense*), mugwort (*Artemisia vulgarism*), cat, orchard, and ragweed.

9.6.3 Total Polyp Score

Polyps will be evaluated in each nostril by means of nasal endoscopy and graded based on polyp size, resulting in scores of 0 to 4 (Appendix 2 [Section 19.2](#)). The TPS is the sum of the left and right nostril scores. The TPS values for efficacy analyses will be determined from blinded central evaluations of nasal endoscopies performed at Screening, on Day -3, pre-dose on Days 21 and 49, and on Days 84, and 112 or ET. Videos of the endoscopies will be evaluated by independent blinded reviewer. The primary endpoint of this study is the reduction in TPS values from Baseline to Week 12 after the start of treatment.

9.6.4 Nasal Endoscopy

Nasal endoscopies (blinded centralized evaluation) will be performed at Screening, on Day -3, pre-dose on Days 21 and 49, and on Days 84 and 112 or ET for efficacy analyses. Videos of the endoscopy will be evaluated by independent blinded reviewer.

9.6.5 Computed Tomography Scan

At selected Investigator sites, CT scans will be performed at Days -3 and 84 or ET to assess size of nasal polyps based on Lund-Mackay score (Appendix 3 [Section 19.3](#)). The CT scans are optional and will only be done at Investigator sites at which appropriate and timely regulatory approval or authorization can be granted.

9.6.6 Peak Nasal Inspiratory Flow

Peak nasal inspiratory flow will be performed pre-dose on Days 0 and 21 and on Day 84 and 112 or ET to assess the extent of nasal airway patency.

9.6.7 University of Pennsylvania Smell Identification Test™

The UPSIT (Appendix 4 [Section 19.4](#)) will be self-administered by patients pre-dose on Days 0, 21, and 49 and on Days 14, 84, and 112 or ET to assess ability to smell.

9.6.8 Sino-nasal Outcome Test-22

The SNOT-22 (Appendix 5 [Section 19.5](#)) will be completed by patients at Screening; pre-dose on Days 0, 21, and 49, and on Days 14, 84, and 112 or ET to assess rhinosinusitis symptoms.

9.6.9 Visual Analogue Scale and Clinical Symptoms Improvement Scale

Visual analogue scales and the clinical symptoms improvement scale³ (Appendix 6 [Section 19.6](#)) will be completed by patients at Screening; at start of Run-in; on Day -3, pre-dose on Days 0, 21, and 49; and on Days 14, 84, and 112 or ET to assess rhinosinusitis symptom severity. The VASs and clinical symptoms improvement scale³ will be completed at clinic visits; however, if the Run-in clinic visit is replaced by telephone contact, the patient will complete the scales at home and bring them to the next (Day -3) clinic visit.

9.6.10 36-Item Short Form Health Survey

The SF-36 (Appendix 7 [Section 19.7](#)) will be completed by patients pre-dose on Days 0, 21, and 49 and on Days 84 and 112 or ET to assess quality of life.

9.6.11 Spirometry

Spirometry will be performed at Screening and pre-dose on Days 21 and 49 to assess FEV1, FVC, and FEF.

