
SECONDARY OBJECTIVES
	
 1. To evaluate the effect of 2 different dose levels of AK001 in combination with an INS versus the INS alone on changes from Baseline to Week 12 after the start of treatment in: 
 a) Size of polyps as evaluated by Lund-Mackay score at selected Investigator sites by computed tomography (CT) scan b) Nasal airway patency as evaluated by peak nasal inspiratory flow (PNIF) c) Ability to smell (University of Pennsylvania Smell Identification Test™ [UPSIT]) d) Patient-reported symptoms of sinusitis (Sino-nasal Outcome Test-22 [SNOT-22] and Visual Analogue Scales [VASs]) e) Clinical symptoms improvement scale f) Quality of life (36-Item Short Form Health Survey [SF-36]) 2. To evaluate the time to first response in TPS 3. To evaluate the change in TPS, UPSIT, and patient-reported symptoms of sinusitis over time 4. To evaluate the safety and tolerability of 2 different dose levels of AK001 in combination with an INS during 7 weeks of study drug in patients with moderate to severe nasal polyps and whose symptoms are resistant to INSs

EXPLORATORY OBJECTIVES
	
In all patients, to:
 
 1. Potentially explore markers of MCs and eosinophils and inflammatory response in blood 
In patients with comorbid asthma, to explore the effect of 2 different dose levels of AK001 in combination with an INS versus the INS alone on changes from Baseline to Week 12 after the start of treatment in:
 
 1. TPS 2. Pulmonary function (forced expiratory volume in 1 second [FEV1], forced vital capacity [FVC], and forced expiratory flow [FEF]) assessed using spirometry 3. Asthma-related symptoms (Asthma Control Test™ [ACT]) 4. Use of asthma rescue therapy

NUMBER OF PATIENTS	Approximately 70 patients randomized to receive 25 mg of AK001 (n=25), 250 mg of AK001 (n=25), or a corresponding placebo (n=20)

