3.3 Exploratory Objectives

The exploratory objectives are to:

1. Potentially explore markers of MCs and eosinophils and inflammatory response in blood

In addition, in patients with comorbid asthma, the exploratory objectives are to explore the effect of 2 different dose levels of AK001 in combination with an INS versus the INS alone on changes from Baseline to Week 12 after the start of treatment in:

1. TPS (Appendix 2 [Section 19.2](#))
2. Pulmonary function (forced expiratory volume in 1 second [FEV1], forced vital capacity [FVC], and forced expiratory flow [FEF]) assessed using spirometry
3. Asthma-related symptoms (Asthma Control Test™ [ACT] Appendix 8 [Section 19.8](#))
4. Use of asthma rescue therapy

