9.6.12 Asthma Control Test™

In patients with comorbid asthma, the ACT (Appendix 8 [Section 19.8](#)) will be completed by patients at Screening; pre-dose on Days 0, 21, and 49; and on Days 84, and 112 or ET to assess the frequency of shortness of breath and general asthma symptoms, use of asthma rescue medications, the effect of asthma on daily functioning, and overall asthma control.

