15 STATISTICAL METHODS AND CONSIDERATIONS

This section outlines the nature and rationale for the statistical methods to be used for the analysis of the data from the study. Baseline will be defined as the last measurement before the patient is randomized. All data will be included in data listings. A separate Statistical Analysis Plan (SAP), which must be documented as completed prior to unblinding the study, will describe data handling and statistical techniques in full detail, except missing PK data handling and PK analysis methods will be described in the PK report. The SAP will contain any modifications to the analysis plan described below in this section.

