15.5 Analysis of Exploratory Endpoints

The exploratory analyses are not powered for statistical significance.

Potentially, markers of MCs and eosinophils and inflammatory response in blood for each active treatment group will be compared separately with the placebo group, with suitable analyses that will be described in the SAP.

Enrollment in this study is designed for presence or absence of asthma as a stratification factor; thus, asthma will be equally distributed among the 3 groups. This stratification factor may be used in the analyses of the primary and secondary analyses described above. Additional exploratory analyses are planned to explore any possible trend in favor of AK001 in the subgroup of asthmatic patients.

In patients with comorbid asthma, use of asthma rescue therapy will be summarized by number and percentage. Changes from Baseline; percentage changes from Baseline; absolute TPS (Appendix 2 [Section 19.2](#)); pulmonary function (assessed using spirometry) as evaluated by FEV1, FVC, FEF; and ACT (Appendix 8 [Section 19.8](#)) for each active treatment group will be compared separately with the placebo group using the same repeated measures model described above, to detect any potential trend at Week 12 and at other visits.

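### The exploratory Week 12 change in FEV1, FVC and FEF has no data behind it: spirometry stops at Day 49

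*Protocol*

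**What the plan says.** **Objective.** The synopsis and Section 3.3 (Exploratory Objectives) each list four items for patients with comorbid asthma. A single lead-in governs all four and asks for the effect of the two AK001 doses against the intranasal steroid alone "on changes from Baseline to Week 12 after the start of treatment in" those items. The second item is "Pulmonary function (forced expiratory volume in 1 second [FEV1], forced vital capacity [FVC], and forced expiratory flow [FEF]) assessed using spirometry".

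**Analysis.** Section 15.5 names FEV1, FVC and FEF, together with TPS and ACT. It compares each active arm with placebo in the repeated measures model, "to detect any potential trend at Week 12 and at other visits".

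**Schedule.** Section 9.6.11 states: "Spirometry will be performed at Screening and pre-dose on Days 21 and 49 to assess FEV1, FVC, and FEF". Footnote 22 to Table 1 repeats that sentence, and the spirometry row of Table 1 is marked in the same three columns only.

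**Baseline.** Section 15 sets the general rule: "Baseline will be defined as the last measurement before the patient is randomized".

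**Status.** Section 15.5 also says: "The exploratory analyses are not powered for statistical significance".

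**The concern.** Two sets of passages cannot both stand. The synopsis, Section 3.3 and Section 15.5 ask for a Week 12 result in lung function. Table 1, footnote 22 and Section 9.6.11 never instruct a site to measure lung function at Week 12. The SAP can choose a model, but it cannot supply a measurement that was not scheduled, and a value not taken at Day 84 cannot be recovered later.

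An existing value does not fill the gap. The Day 49 spirometry is taken before that day's infusion, so it precedes the third of the three doses (Days 0, 21 and 49). A Week 7 result therefore answers a different question from a Week 12 result. If a Day 49 value were reported as Week 12, the reader would be misled about how much treatment preceded the measurement.

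**Working it through.** **1. Which visits have spirometry.** Table 1 labels Day 21 as Week 3, Day 49 as Week 7 and Day 84 as Week 12. Reading its rows across:

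| Measure | Scheduled at |
|---|---|
| Spirometry | Screening, Day 21, Day 49 |
| ACT | Screening, Days 0, 21, 49, 84, 112 |
| PNIF | Days 0, 21, 84, 112 |

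The spirometry row, footnote 22 and Section 9.6.11 agree with each other, so the gap does not come from a badly read table. Section 9.6.12, for the other asthma questionnaire measure under the same lead-in, does include Week 12: "and on Days 84, and 112 or ET to assess the frequency of shortness of breath".

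**2. Distance from the last spirometry to Week 12.** The windows in Table 1 are Day 49±2 and Day 84±4.

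- Nominal: 84 − 49 = 35 days
- Shortest: (84 − 4) − (49 + 2) = 80 − 51 = 29 days
- Longest: (84 + 4) − (49 − 2) = 88 − 47 = 41 days

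No combination of permitted windows brings a Day 49 measurement near Week 12.

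**3. Whether the Week 12 contrast can be estimated.** Take an arm-by-visit model with 3 arms and post-baseline visits at Days 21, 49 and 84. This has 3 × 3 = 9 cell means. The contrast L is active minus placebo at Day 84. It is estimable only if adding L to the design matrix X leaves the rank unchanged.

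- As scheduled (Days 21 and 49 only): rank(X) = 6 and rank([X; L]) = 7, so the contrast is not estimable.
- With Day 84 spirometry: rank(X) = 9 and rank([X; L]) = 9, so it is estimable.

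**4. Whether imputation helps.** Section 15.3 states last and worst observation carried forward for the primary endpoint only. Carrying Day 49 forward for lung function would replace the Week 12 value in every patient. That is absence by design, not missing data, and the result would be the Week 7 contrast under another name.

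**5. Whether other measures share the problem.** Measures with a Week 12 objective that are collected at Day 84 are TPS, Lund-Mackay CT (selected sites only), PNIF, UPSIT, SNOT-22, VAS, the clinical symptoms improvement scale, SF-36, ACT, and asthma rescue therapy (through the concomitant medication record). That makes 10. Spirometry is the eleventh and the only one without a Day 84 assessment.

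**6. What remains possible.** Changes at Week 3 and Week 7 can be compared. Under the Section 15 rule, Baseline for spirometry is the Screening value, because no later spirometry precedes randomization. That value is taken before the 4-week NASONEX run-in.

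**The case against.** The strongest objection concerns weight. This is one of four exploratory items in a subgroup, the protocol says the analyses are unpowered and look only for a trend, and lung function still has two post-baseline visits. All of this is true. It keeps the point below the critical level, but it does not remove the contradiction.

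Second, the Week 12 phrase in Section 15.5 closes one sentence shared by TPS, lung function and ACT. It could be read as meaning each measure at whatever visits it has. Section 15 also lets the SAP modify the analyses described there. So the Section 15.5 part could be repaired without a protocol amendment. That does not reach the synopsis and Section 3.3, which lie outside Section 15 and name Week 12 explicitly as the time point for lung function.

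Third, nothing in the protocol shows which side is the mistake. ACT is under the same Week 12 lead-in and is measured at Day 84, so an omission from the schedule is as plausible as a wrong time point in the objective. This stands. The choice between the two repairs belongs to the sponsor.

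Fourth, the count of measures with Day 84 data includes CT, which is optional, and rescue therapy, which has no dedicated Day 84 assessment. That is fair. The count is context only, and the finding rests on the absent Day 84 spirometry.

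**Conclusion.** The concern holds. As written, the protocol states an exploratory objective and plans a comparison for three variables (FEV1, FVC, FEF) at a visit where none of them is measured. The last scheduled value precedes that visit by 35 days nominally, and by 29 to 41 days within the windows, and it comes before the third infusion.

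The conclusion assumes that sites follow Table 1. Occasional unscheduled spirometry near Day 84 would not give a planned, comparable estimate across arms. The consequence is limited to this objective: the primary TPS analysis, the secondary endpoints and the safety conclusions are unaffected, and the Week 3 and Week 7 lung function comparisons remain feasible. It should be corrected, but it does not threaten the trial.

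**What to change.** Reconcile the passages in one of two ways.

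**Change the wording to match the schedule.**
- In the synopsis and Section 3.3, take lung function out of the shared Week 12 lead-in and state its objective as change from Baseline to Day 49 (Week 7).
- In Section 15.5, state the spirometry contrast at Week 7, with Week 3 as the other visit.
- State that Baseline for spirometry is the Screening value, taken before the run-in.
- Leave TPS, ACT and rescue therapy at Week 12.

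The cost is text edits in three places plus the Baseline sentence. No procedure is added.

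**Or change the schedule to match the objective.** If the sponsor wants Week 12 to remain the lung function question, Table 1, footnote 22 and Section 9.6.11 must all include Day 84. This adds one spirometry per patient at an existing visit. The number is at least 0.50 × 70 = 35 patients if limited to those with asthma (the protocol's 50% floor on about 70 patients). It is up to about 70 as the schedule now reads, because footnote 22, unlike footnote 23 for ACT, is not restricted to patients with asthma. This route only works if it is settled before patients pass Day 84.
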